All email correspondence will occur in accordance with BIDMC guidelines. Once the signed consent form has been received by the investigator, he/she will then sign, date, and time the form. No study procedures will occur before the consent form has been signed by both the surrogate and the investigator. The surrogate will be instructed to return the original signed consent form to BIDMC which will be kept in the subject's research record with the electronically transmitted copy and a detailed note to file.

In the rare event that a physician Investigator is not physically present in the hospital to perform the consent process (for example, overnight) and given the time-sensitive nature of this trial, a research assistant will coordinate a video conference (ie, FaceTime) between the physician investigator, the patient or LAR, and the research assistant; the physician investigator will perform the consent from a remote location. The physician investigator will subsequently sign the paper copy; in the interim, the research assistant will sign the consent, in addition to the patient or LAR, and that signed copy will be included in the patient's medical record and as well as be provided to the study subject.

Once the patient is enrolled in the trial, the study MD enters a note in the patient's medical record documenting the enrollment. Only after the consent form is signed by both the family/HCP and the investigator, will study procedures take place. In obtaining and documenting informed consent, each investigator will comply with the applicable regulatory requirements and adhere to the ethical and Good Clinical Practice principles that have their origin in the Declaration of Helsinki. The consent must be the Institutional Review Board (IRB)-approved version corresponding to the version of the protocol approved when the screening was initiated.

Subject Protection

There will be no undue influences on the potential study subjects to participate. No subjects will be vulnerable to coercion or undue influence. Patient information will be encrypted and stored on password protected computers, therefore minimizing the risk of their privacy being compromised.

[name] will also periodically review the data to evaluate subjects' safety and data integrity. The purpose is to determine whether study subjects are exposed to unreasonable risk because of study participation, and to monitor study progress and integrity. [name] will

review and report all adverse events to the Committee on Clinical Investigation (CCI) according to the adverse event reporting policy of the CCI.

All biological material will be stored in a locked refrigerator/freezer within a locked facility, which is under hospital security surveillance at all times. All electronic records will be maintained on BIDMC IS compliant computers.

B7. STUDY LOCATION

Privacy

In order to maintain privacy, the investigators will discuss the study and consent the subjects in a private area in-hospital. Standard clinical protocols regarding patient confidentiality will be followed during the course of the study. The collection of sensitive information about subjects is limited to the amount necessary to achieve the aims of the research.

Physical Setting

The study will take place in the Emergency Department and ICUs at Beth Israel Deaconess Medical Center and Lahey Hospital & Medical Center in Burlington Massachusetts.

B8. DATA SECURITY

All hard copies of study data will be kept in a locked filing cabinet to which only the PI and co-investigators will have access.

All electronic data will be stored on the BIDMC secure server behind a firewall in a password-protected database. We will also utilize the database application, REDCap. REDCap is a professional database endorsed by the National Institutes of Health (through the clinical and translational science award) that provides a secure, user-friendly database with capacity for easy statistical analysis. The program can support multiple research studies, is presently being used at dozens of major academic research centers to support numerous NIH and AHA funded projects and is available for free at our center.

B9 Multi-Site Studies

Is the BIDMC the coordinating site? Yes No

Is the BIDMC PI the lead investigator of the multi-site study? Yes No

Coordinating Center (BIDMC) Responsibilities: The trial will be directed by the Principal Investigator, who will have responsibility for receiving and analyzing data for the trial, and will oversee all functions. We will provide the other institutions with documents to use and communicate procedures.

As the coordinating center for this multicenter trial, [name] assumes full responsibility for ensuring all aspects of the study are conducted appropriately. This will be achieved via the following mechanisms, under the direction of [name]:

1. Coordinating center (the Center for Resuscitation Science – CRS) will receive a copy of the screening log from Lahey Hospital & Medical Center on a monthly basis

2. At a minimum, quarterly conference calls will be held with Lahey Hospital & Medical Center site PI/research coordinator to discuss study progress
3. Any questions or problems that arise during an enrollment will be addressed in real time through direct communication between Lahey Hospital & Medical Center staff and the CRS. The study PI will be available to Lahey Hospital & Medical Center site PI for consultation 24/7 via cell phone/email.
4. CRS staff will track and report all serious adverse events and unanticipated problems
5. CRS will provide periodic updates to affiliated investigators on participant enrollment, general study progress, and relevant scientific advances
6. CRS staff will ensure that all relevant IRB correspondence (continuing review amendments) and study status changes are communicated to Lahey Hospital & Medical Center
7. CRS staff will document receipt, shipment and storage of study specimens
8. Data management: Study enrollment data will be entered into RedCap directly by Lahey Hospital & Medical Center research staff. HPI (name, MRN, etc) will not be available to BIDMC staff. In order to ensure strict data integrity, CRS staff will perform data checks in the REDCap database.
9. The study PI will be personally notified within 24 hours of any serious adverse event and will receive a copy of the AE form submitted to Lahey Hospital & Medical Center IRB within a week of the event
10. PI will be personally notified within 24 hours of a protocol deviation and will receive a copy of the deviation form submitted to the Lahey Hospital & Medical Center IRB.
11. We will conduct an in-person site visit after every 20 enrollments or earlier on an as needed basis. During these site visits, we will assess research study progress and compliance with the IRB approved protocol and procedures. This will include review of source documents for key data elements.
12. As part of our on-site visit, we will include a Lahey Hospital & Medical Center Research Pharmacy review to assess the following: documentation of secure drug storage; drug accountability from receipt of drug through all dispensing and ultimately destruction on drug accountability logs; documentation of performance of regular inventory verification; confirmation that orders for research medication are written only by authorized prescribers on the 1572 form or delegation of authority log; confirmation that study drug must have continuous temperature monitoring and recorded at least daily on temperature logs (minimum, maximum, current); verification of drug destruction per Lahey Hospital & Medical Center internal policy. The BIDMC Research Pharmacy will be available to answer questions as they may arise from the Lahey Hospital & Medical Center Research Pharmacy.
13. A formal site monitoring report will be provided to Lahey Hospital & Medical Center and the CCI after each site visit. This report will include data on the number of charts reviewed, discuss any identified deficiencies and any corrective actions taken. The Lahey Hospital & Medical Center site PI will then provide this report to their local IRB in accordance with local IRB reporting requirements.

Database Management: The coordinating center (BIDMC) will be responsible for developing the online database (see section 4.4), including a shared database with common data definitions. All forms and data dictionary will be available online for all individuals who perform data entry.

All sites will enter de-identified data into the electronic database. Data entry will be done via REDCap. Discrepancies or missing data points will be identified through a data review process by the coordinating center resulting in queries sent to the participating sites for resolution. Changes will be made in REDCap by each participating site.

The coordinating center will oversee and instruct sites on specimen collection and separation. Sites will be provided with detailed instructions for laboratory processing. All sample types will be processed initially on site, separated by centrifugation if necessary, dispensed into aliquots if required, and kept frozen (preferable at -80°) until shipment to the Center for Resuscitation Lab .

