2.2 Significance

2.2a. Overall significance of the current proposal: Given the sheer numbers of patients afflicted with septic shock each year, and the current mortality rates despite advances in early aggressive treatment and sophisticated critical care, new targets are needed in the armamentarium against this disease. With the ageing of the U.S. population, it is anticipated that the incidence of sepsis and septic shock will only increase¹, adding to the urgency to identify an intervention to improve outcomes and reduce disease burden amongst survivors.

2.2b. Innovation: The current proposal is innovative in that it leverages an existing therapeutic agent for a new indication, building on existing data supporting the concept of beta-adrenergic antagonism in septic shock. If the promising findings reported in the recent single center study from Italy⁶ could be confirmed in a pilot study in a septic shock cohort in a typical U.S. tertiary care medical center, the science of the resuscitation of septic shock could be considerably advanced. Esmolol, which is already used in practice in other clinical scenarios in critical care, could easily be incorporated into the treatment of patients with septic shock, if the balance of evidence ultimately indicates benefit in this population. In addition to evaluating the effects of esmolol on hemodynamics, our proposal is innovative in that we will also directly measure continuous VO_2 in the subset of patients who are mechanically-ventilated in order to better understand how beta blockade therapy will affect overall oxygen consumption in a septic shock population, which to our knowledge has not been previously examined in this way.

B3. DESCRIPTION OF RESEARCH PROTOCOL

[figure not shown]
A. Study Design – Overview, Methods, Procedures

Study Design: A Multi-center, open-label, randomized, phase II trial comparing esmolol to standard care (no esmolol) in septic shock patients with tachycardia.

Screening: All patients admitted to the ICU will be identified through electronic patient records and screened for possible enrollment by trained research assistants. Our research group employs multiple full-time research assistants responsible for screening and enrollment. With this staffing structure, we are able to enroll patients 24 hours per day/7 days per week.

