Consent: If a patient meets all of the inclusion criteria and none of the exclusion criteria, a member of the research team will approach the patient for written informed consent. If the patient is unable to consent, a legally authorized surrogate may be approached per standard IRB procedures. Investigators will explain the study's background and significance, potential risks and benefits, and study protocol. In the event that a physician Investigator or a surrogate is not physically present in the hospital to perform the consent process, a non-physician study staff (research assistant or research coordinator) will coordinate a conference (i.e. FaceTime or Skype video conferencing or telephone) for the physician investigator / surrogate to join in the consent discussion. If consent is obtained, a signed copy will be given to the patient and another copy placed in the medical record. The original signed informed consent will be kept in our locked research office (see specifics in **Section B6 - Recruitment and Consent Procedures**).

Randomization: The randomization will be done in a 1:1 ratio between treatment and control groups in varying blocks of two to six using SAS software. This main list of group assignment will be maintained in the hospital research pharmacy.

Study Arms: After randomization as described above, patients will be assigned to one of the following two arms: esmolol for 24 hours or standard care (no esmolol).

1) Esmolol for 24 hours: Patients in this arm of the study will have Esmolol for 24 hours.

2) "Usual Care": Patients will receive 100 mL of normal saline over 5-10 minutes at the beginning of the study in addition to usual care. When patients are enrolled in a clinical trial there is a time period from consent to study drug administration that depends on the investigative team, the research pharmacy, and the available nursing staff. In order to guarantee that this time interval is similar between the two groups the control arm will receive a small bolus of saline at the beginning of the trial. This will ensure that "time zero" is similar between the two groups.

Blinding: The study will not be blinded as an esmolol infusion must be actively titrated to effect by clinicians and it will noticeably decrease heart rate.

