Standard septic shock treatment: Patients, irrespective of treatment group, will be managed at the discretion of the clinical team. BIDMC has internal guidelines for the management of septic shock which reflect the most recent 2012 Surviving Sepsis Campaign guidelines and are incorporated into the care of patients with septic shock in the ICUs.²³

Study medication preparation and administration: After consent and enrollment, a form will be faxed to the pharmacy confirming the consent, indicating the specific study, and supplying information on the location of the patient. An electronic order will be placed in the computer to initiate the study drug. Telephone contact will be made with the pharmacist to confirm receipt and execution of the study medication protocol. Enrolled patients will be randomized to either esmolol or standard care (see above). The study drug will then be sent to the ICU and will be administered to the patient by the treating nurse. Esmolol will be titrated to a heart rate of 80 - 94 per minute, starting at 10mcg/kg/min and subsequently increasing every 20 minutes in increments of 10 mcg/kg/min (or slower at the discretion of the team) until target is achieved. The maximum allowed dose will be 300mcg/kg/min. Esmolol will be continued for 24 hours.

If the patient is randomized to standard care, a one-time 100 mL saline placebo will be administered as a time stamp for the study protocol.

Rationale for dosage regimen: The dosing regimen chosen for this study is similar to that described in the study by Morelli *et al.*⁶ In that study, the median esmolol dose was 100mg/hr (IQR 50-300), and they did not exceed a maximum of 2000mg/hr. At BIDMC, we administer esmolol via a weight-based protocol, and for an average 70kg patient, the mean dose would not be expected to exceed the maximum dose used in the Morelli *et al.* study, therefore helping to ensure safety. Since esmolol is titrated, we will have a titration protocol that will be utilized by the

bedside nurse in the ICU to adjust the infusion based on target heart rate parameters.

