(4) There is the risk of loss of confidentiality. However, none of the participant's protected health information will be shared with any of the other sites. In addition, all measures will be taken to ensure that no confidential information is released. All data will be kept on password protected computers behind the BIDMC firewall. The data safety and monitoring board (DSMB) will provide a multidisciplinary, independent review of the study design, ethical and scientific conduct of the study, monitor interim results and make recommendations with respect to continuation, modification, termination of study. Each individual is an experienced academician and together will provide clinical, research, and statistical expertise. The DSMB will meet at planned interim analyses for safety, at completion, and at any other needed interval.

We do not anticipate any psychological risks of participating in the study. There will be no financial risks associated with study participation.

B6. RECRUITMENT AND CONSENT PROCEDURES

Recruitment

Potential subjects will be evaluated for eligibility by the research team. Some of these patients may be critically ill and unable to provide informed consent. However, due to the severity of their illness, most of these patients will have family members or their health care proxy (HCP) in attendance. If the patient is unable to consent for themselves, consent may be obtained from a legally authorized representative (LAR).

Before the patient or surrogate is approached for consent, the case is reviewed by the study MD (PI or Co-investigator) to ensure that the patient is appropriate for inclusion in the trial. Additionally, the physician on the clinical team caring for the patient is contacted as well, to ensure that the clinical team authorizes approaching the patient/surrogate for consent.

Consent

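### Short permuted blocks in an open-label trial let anyone who tracks a whole allocation list guess about 70% of next assignments, and the unadjusted 6-hour primary test would not remove selection made on those guesses

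*Protocol*

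**What the plan says.** Protocol section B3.A, Randomization: "The randomization will be done in a 1:1 ratio between treatment and control groups", "in varying blocks of two to six using SAS software". On custody of the list, the same paragraph says "This main list of group assignment will be maintained in the hospital research pharmacy". Under Study medication preparation and administration, the pharmacy is brought in late: "After consent and enrollment, a form will be faxed to the pharmacy confirming the consent".

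Under Blinding: "The study will not be blinded as an esmolol infusion must be actively titrated to effect by clinicians". Past assignments are therefore visible at the bedside.

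Under Screening, ICU patients are "screened for possible enrollment by trained research assistants". Section B6, Recruitment, adds two judgements before the approach for consent. First, "the case is reviewed by the study MD (PI or Co-investigator) to ensure that the patient is appropriate for inclusion in the trial". Second, the treating physician is contacted "to ensure that the clinical team authorizes approaching the patient/surrogate for consent".

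The SAP (Statistical Analyses) tests the primary endpoint, norepinephrine equivalent dose (NED) at 6 hours, with a Wilcoxon rank-sum test and no baseline adjustment. Its repeated-measures model for 12 hours and the trend does adjust for pre-intervention NED. Protocol section B7 names two sites. Neither document states the mix of block sizes, or whether the list is stratified by site.

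**The concern.** Keeping the list in the pharmacy hides the next code but not the running count. In permuted blocks the arms return to balance at the end of every block, so the arm that is behind is more likely to come next. With blocks of at most six this happens often.

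A guess does harm only if someone can act on it before randomization. The case review and the clinical team's approval are points where judgement enters. If patients approached when esmolol looks due differ in vasopressor need from those approached when control looks due, the arms differ at baseline. Baseline dose is likely to be related to dose at 6 hours, and an unadjusted test passes that difference into the primary result.

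**Working it through.** **Inputs from the documents.** 1:1 allocation and block sizes two to six (Protocol B3.A); 1:1 requires even sizes, so 2, 4 and 6. N = 104, SD 0.09, planned difference 0.15 − 0.10 = 0.05 mcg/kg/min, 80% power, alpha 0.05 (SAP).

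**The plan's own figure.** A two-sided two-sample t-test with difference 0.05 and SD 0.09 needs 51.84 per arm, so 52 per arm or 104 in total. The stated N is reproduced and does not depend on this point. The documents state no guessing rate; the rates below are derived.

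**Guessing rate with the whole list seen.** Rule: guess the arm that is behind and toss a coin when tied. Expected correct guesses in a block of 2b are b + (4^b / C(2b,b) − 1)/2.

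- Size 2: 1 + (4/2 − 1)/2 = 1.5 of 2, or 75.0%
- Size 4: 2 + (16/6 − 1)/2 = 2.833 of 4, or 70.8%
- Size 6: 3 + (64/20 − 1)/2 = 4.1 of 6, or 68.3%
- Sizes equally likely per block (assumed): (1.5 + 2.833 + 4.1)/12 = 8.433/12 = 70.3%
- Equal patient share per size (assumed): (75.0 + 70.8 + 68.3)/3 = 71.4%

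Any mix lies between 68.3% and 75.0%. Simulation at N = 104 with equally likely sizes gives 70.2%. One arm is behind at 59% of allocations, and that guess is right 84% of the time: 0.59 × 0.84 + 0.41 × 0.5 = 0.70. The same 59% can be called with at least 75% confidence by someone who knows the sizes. About 4% are certain to that person.

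**Guessing rate with part of a shared list seen.** Under the same rule (simulated, shares assumed): 58.8% if 90% of the sequence is seen, 56.5% at 80%, 53.3% at 50%.

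**What drives the rate.** The rule uses no knowledge of block sizes, so withholding them leaves 70.3%. A fixed block of six still gives 68.3%. Sizes 4/6/8 give (2.833 + 4.1 + 5.329)/18 = 68.1%.

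**Possible effect on the primary test.** Assume staff move the enrolled dose by plus or minus η in line with the guess, with full carry-over to 6 hours. For guessing rate p, bias = 2η(2p − 1). The standard error is 0.09 × √(2/52) = 0.01765. Type I error is the chance that a normal variable centred at bias/SE lies beyond ±1.96. With p = 0.703:

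| η (mcg/kg/min) | Bias | Bias/SE | Type I error |
|---|---|---|---|
| 0.01 | 0.0081 | 0.46 | 7.5% |
| 0.02 | 0.0162 | 0.92 | 15.1% |

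A bias of 0.0162 is 32% of the planned 0.05. At η = 0.02 with p = 0.533 to 0.588 for all patients, type I error is 5.3% to 6.8%. These figures use the normal approximation for a comparison of means, as in the sample-size calculation.

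**Alternatives.**

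- Blocks 4/6/8: 68.1% correct, but calls at 75% confidence or more fall from 59% to about 34–35%. At η = 0.02, bias is 0.0145 and type I error 13.0%.
- Big-stick list with maximum imbalance 3: in the long run the walk sits at its limit 2/12 = 16.7% of the time, so 16.7% of allocations are forced. Correct guesses are 0.167 × 1 + 0.833 × 0.5 = 58.3% (58.1% simulated at N = 104). At η = 0.02, bias is 0.0065 and type I error 6.6%.

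**The case against.** Varying permuted blocks are conventional, and the protocol has real safeguards: pharmacy custody, contact only after consent and enrolment, and round-the-clock screening of ICU admissions by several research assistants. These stand. They keep the next code undisclosed, but they do not hide the count of past assignments.

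The size of harm is assumed. A shift of plus or minus 0.02 means that patients enrolled under the two guesses differ by 0.04, or 0.44 SD, which is 80% of the planned effect. Every favoured guess must be acted on, and the shift must carry over fully to 6 hours. With half carry-over, the 15% becomes 7.5%. This stands too, so the error rates are illustrations.

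A second site dilutes the guess if the list is shared. That is correct. However, the amendment forms show that the current second site was approved only on 11/28/2017, with local IRB approval dated 04/03/2018, against a protocol dated January 2015. An earlier added site was later removed, and its enrolment is not given. Much of accrual may have been at one site, where 70% applies; a list per site gives the same rate.

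The SAP reports that baseline covariates appeared balanced. It does not name NED, and a difference of 0.016 is 0.18 SD, less than the standard error of √(2/52) = 0.20 SD. Apparent balance could not rule it out.

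A reader might infer that the block of two or the printed sizes create the problem. The arithmetic does not support that: the guessing rule needs no sizes, a fixed block of six still gives 68.3%, and knowing the sizes makes only about 4% of allocations certain.

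**Conclusion.** The point holds as a risk. Short blocks with visible past allocations give about 70% correct guesses (68% to 75% over any mix of sizes) against 50% by chance, for someone who sees the whole list. On a shared list partly seen, the rate is about 53% to 59% under assumed shares. The documents do not settle which case applies.

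The judgements before consent make selection possible, and the unadjusted 6-hour test would not correct the resulting imbalance. Type I error of about 7% to 15% requires the 70% rate, an assumed shift of plus or minus 0.01 to 0.02 mcg/kg/min and full carry-over.

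Two stronger inferences are not supported. The documents do not show that anyone selected patients by expected arm. Nor do they show that the trial's type I error is 15%; that figure is conditional on a behaviour that nobody has reported.

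**What to change.** **If allocations remain**, replace the list with a less predictable one, generated by someone outside enrolment. There are two options:

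- Larger random blocks without size two, such as 4/6/8. The rate falls only to 68%, but high-confidence calls drop from 59% to about 34–35%.
- A maximum-tolerated-imbalance list such as big-stick with limit 3. Correct guesses fall to 58% with the same maximum imbalance of 3 as a block of six. The downside is that about 17% of allocations are forced, and so certain to someone who knows the rule, against about 4% now.

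Either way, keep the details in a restricted pharmacy or statistician file and state in the protocol whether lists are per site. Hiding the sizes alone leaves the 70% unchanged. The cost is one new list, one amended sentence and, with either option, slightly looser balance at intermediate points than blocks of two give.

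**If enrolment is closed**, as the past-tense SAP of December 2020 suggests, report the 6-hour comparison adjusted for pre-intervention NED beside the Wilcoxon test, and disclose the allocation scheme as a limitation. The SAP already uses pre-intervention NED in its longitudinal model, so no new data are needed. Adjustment deals with selection on recorded dose, but not with selection on unrecorded features.
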